4.6. Prior and Concomitant Medications

Medications reported from 7 days before first dose of study drug and up to last contact date will be summarized by preferred term using the World Health Organization-Drug Dictionary for the ITT-i Set and the Safety Set as frequency tables in 2 parts:

1. Prior medication: medication that started before the first dose of study drug, regardless of when dosing of the medication ended
2. Concomitant medication: medication received at or after the first dose of study drug, medication that was received before initial dosing and continued after initial dosing of study drug, or medication with missing stop date.

(Medication that started before the first dose of study drug and continued after the first dose of study drug will be summarized as prior medication and separately as concomitant medication.)

A frequency tabulation of concomitant medication will be shown by ATC class level up to level 3. Frequency tabulations will be made for concomitant antibiotics, type of SOC, corticosteroids, and medication administered to treat COVID-19 infection by ATC class and by hospitalization status. Additionally, tabulations will be made of concomitant corticosteroids and antibiotics administered because of adverse events reported as influenza complications.

The ATC level 2 code J01 will be used to identify concomitant antibiotics.

The ATC level 2 code H02 and the ATC level 4 codes M01BA, R03BA, and R03AK will be used for identifying corticosteroids. Separate frequency tabulations will be made for antipyretic medication and oxygen supplementation. The ATC level 4 codes N02BA and N02BE and the generic medication names paracetamol, ibuprofen, and acetylsalicylic acid will be used to identify antipyretic medications. The table showing oxygen supplementation will be tabulated per analysis visit, phase and treatment subperiod. If a prior/concomitant therapy record misses components of its start and/or stop dates (time and/or day and/or month and/or year), the following actions will be taken:

1. In case of partial start or stop datetimes, the concomitant therapy records will be allocated to prior and/or concomitant using the available partial information, without imputations.
2. In case of a completely missing start date, the prior and/or concomitant therapy will be considered as having started before the trial.

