Total time in intensive care unit (ICU) stay (hours) [Duration]	
The total number of hours a subject stayed in ICU during the period from first intake until study termination, calculated as sum of [(end date and time of discharge-- start date and time of admission)/3600], rounded to one decimal for all separate events per subject
 
In case ICU admission took place before first intake or in case the start datetime of ICU is missing, then the date and time of first intake will be used.
 
In case the ICU stay ended after the end of the trial or in case the end datetime of ICU stay is missing, then the end datetime of last contact date will be used.
 
If time of the start of ICU admission is missing then use 00:00. If time of the end of ICU admission is missing then use 23:59. The derivation of total time in ICU is analogous to “total length of hospital stay”.

Type of supplemental oxygen administration	
Tabulation will be done as collected per CRF page “Oxygen Supplementation”. In addition, the following categorization will be done:
 
 - Invasive Mechanical Ventilation - Non-Invasive Mechanical Ventilation - Non-Invasive, Non-mechanical Ventilation - None
Mechanical ventilation during study	
Incidence of mechanical ventilation (invasive or non-invasive) Categories:
 
 - Mechanical ventilation at baseline - First administration of mechanical ventilation post-baseline - No administration of mechanical ventilation
Mechanical ventilation started post-baseline	
Incidence of post-baseline mechanical ventilation (invasive or non-invasive)
 
 - Started post-baseline - Not started post-baseline 
Note: In case mechanical ventilation is present at baseline and a second episode of mechanical ventilation is initiated post-baseline, this subject will be counted as started post-baseline.

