Hospital recovery scale outcome assessed on Day 2 to 14 excluding Day 6	
The hospital recovery scale outcome defined per day for Day 2 to 14 excluding Day 6 is defined analogous to the primary endpoint.

Fundamental Hospital recovery scale outcome assessed on Day 2 to 14	
The fundamental hospital recovery scale reflects the status of the subject objectively independent of the opinion of the investigator (irrespective of being ready for discharge or requiring ICU level of care). The Fundamental hospital recovery scale outcome assessed on Day 2 to Day 14 is defined as follows:
 
 6. Death 
 – Subject died at any time on the day of assessment or earlier (all-cause mortality). 5. On invasive mechanical ventilation 
 – Invasive mechanical ventilation is used at any time on the day of assessment. 4. In ICU 3. Non-ICU hospitalization, on supplemental oxygen 
 – Non-ICU hospitalized on the day of assessment (including readmittance) and the subject is on supplemental oxygen. On supplemental oxygen is defined by: 
 – Receiving supplemental oxygen through a face mask or nasal cannula. 2. Non-ICU hospitalization, without supplemental oxygen 
 – Non-ICU hospitalized on the day of assessment (including readmittance) 1. Not hospitalized 
 – Discharged from the hospital before the day of assessment .
Incidence of antibiotic treatment	
Did the subject use antibiotic treatment after first dose of study drug?
 
Categories will be Yes (1) or No (0). The derivation of the categories will be based on the ATC level 2 categorization of concomitant medications. Concomitant medications coded as “J01” will be indicated as antibiotic treatment.

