
Duration of antibiotic treatment (hours) [Duration]
	
The total number of hours a subject used antibiotic treatment (= event) during the period from first intake until study termination, calculated as sum of [(end date and time of event – start date and time of event)/3600], rounded to one decimal for all separate events per subject.
 
In case the start datetime is entirely or partially unknown and the medication was used before start of first intake the date and time of first intake will be used.
 
In case the end datetime is entirely or partially unknown and the medication was used after the trial ended, the last contact date will be used to calculate the duration.
 
If time of the start antibiotic treatment is missing, then use 00:00. If time of the end of antibiotic treatment is missing, then use 23:59The derivation of the duration is analogous to “Total length of hospital stay”.

Time to NEWS2 <= 2 (hours) [Time- to event]
	
The time (hours) from first study drug to first time NEWS2<=2 maintained for 24 hours i.e. the time of the first of at least 2 consecutive NEWS2 assessments with 24 hours in between.
 
If time is missing for the NEWS2, but timepoint is available then time will be imputed: if morning then time will be 08:00, if midday then time will be 12:00, if evening then time will be 20:00.
 
Subjects that did not maintain a NEWS2<= 2 for 24 hours until completion of the trial or withdrawal, will be censored at the time of completion of withdrawal of the study. If time is not available then it will be imputed with 23:59.
 
If the subject died before having a NEWS2 <=2 for 24 hours, the subject will be censored at the maximum time of all subjects.

Time to clinical improvement (hours) [time- to event]
	
The time (hours) from first study drug to clinical improvement. Clinical improvement is defined as the minimum of the time to hospital discharge or time to NEWS2 <=2 maintained for 24 hours.
 
Censoring will be done similarly as ‘time to hospital discharge’ and ‘time to NEWS2<=2’.

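### The antibiotic incidence endpoint counts drugs already running at first dose, which dilutes any effect on new starts, and the duration formula has no rule for concurrent drugs

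*SAP*

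**What the plan says.** **Incidence.** SAP 5.3.1.1 defines incidence of antibiotic treatment by the question "Did the subject use antibiotic treatment after first dose of study drug", answered Yes or No. On the data source it states: "The derivation of the categories will be based on the ATC level 2 categorization of concomitant medications", with code J01 marking an antibiotic. SAP 4.6 includes among concomitant medications "medication that was received before initial dosing and continued after initial dosing of study drug, or medication with missing stop date", and treats a completely missing end date as ongoing at the end of the trial. SAP 5.3.2.1 puts every subject in the analysis set in the denominator. The Firth logistic model in SAP 5.3.2 contains treatment and the stratification factors: NEWS2, antiviral content of standard of care, and time since symptom onset.

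For ICU admission and for mechanical ventilation, SAP 5.3.1.1 adds a separate parameter for episodes that began post-baseline. There is none for antibiotics.

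**Duration.** The same section defines duration as "The total number of hours a subject used antibiotic treatment (= event) during the period from first intake until study termination", computed as a sum of end minus start, "rounded to one decimal for all separate events per subject", and calls the derivation analogous to total length of hospital stay. First intake replaces the start under this condition: "In case the start datetime is entirely or partially unknown and the medication was used before start of first intake".

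**The concern.** The population makes antibiotic use at first dose plausible. Protocol 4.1 requires hospitalization together with hypoxia or invasive ventilation, and its examples of reasons for admission include radiological lower respiratory tract disease and septic shock. Antibiotics are not among the disallowed therapies in Protocol Section 8. A subject whose antibiotic is running at first dose and continues is fixed as a Yes before pimodivir can act. If there are many such subjects, a real reduction in new starts could be lost in the overall percentage, and a null result could not be told apart from pre-study prescribing.

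For duration, the hospital-stay formula needs no merge rule because hospital stays do not overlap. Antibiotics can overlap. Protocol Section 8 records type, treatment period and regimen for each therapy, so a programmer may well treat each drug record as an event. The result would then be summed drug-hours, not hours on antibiotic treatment.

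**Working it through.** **The plan's own figure.** The only design calculation is for the primary endpoint: 600 subjects, 90% power, 38% reduction in the common odds ratio, two-sided 5% (SAP 1.4 and 5.1.1). With the stated placebo distribution 30/30/25/5/5/5% and an odds ratio of 0.62, the pimodivir distribution is 40.9/29.9/19.4/3.4/3.3/3.2%. The Whitehead formula N = 12(1.960 + 1.282)² / [ln(0.62)² × (1 − Σp̄³)], where p̄ is the mean of the two arms in each category, gives N = 601.4, and 89.9% power at 600. The figure reproduces and this point does not touch it. No rate, effect or power is stated for the antibiotic endpoints.

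**Incidence.** Let b be the share on antibiotics at first dose and continuing (equal between arms in expectation), and r the new-start rate among the rest.

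- Endpoint as written: P = b + (1 − b)r.
- Difference between arms: (1 − b)(r_placebo − r_pimodivir).

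Neither b nor r is in the documents, so both are assumed. Power uses the normal approximation for two proportions at two-sided 5%: Φ[(Δ − 1.96·se₀)/se₁], with se₀ pooled and se₁ unpooled. The as-written endpoint has n = 300 per arm; an analysis of baseline non-users has 300(1 − b).

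Assumed new starts 30% versus 20% (odds ratio 0.58 among non-users):

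| b | As written | Odds ratio | Power | Non-users per arm | Power in non-users |
|---|---|---|---|---|---|
| 0% | 30% vs 20% | 0.58 | 81% | 300 | 81% |
| 30% | 51% vs 44% | 0.76 | 40% | 210 | 66% |
| 50% | 65% vs 60% | 0.81 | 24% | 150 | 52% |
| 70% | 79% vs 76% | 0.84 | 14% | 90 | 34% |
| 90% | 93% vs 92% | 0.87 | 7% | 30 | 14% |

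Worked row, b = 50%: 0.5 + 0.5 × 0.30 = 0.65 and 0.5 + 0.5 × 0.20 = 0.60. The difference is 0.05, which is half of 0.10. In the last cell, unpooled variance throughout gives z = 0.90 and about 15%.

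With new starts of 20% versus 10%, as-written power at b = 30/50/70/90% is 42/24/13/6%, against 82/68/47/19% in non-users. The odds ratio moves from 0.44 among non-users to 0.75/0.81/0.85/0.88 as written.

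**Duration.** If an event is a drug record, two J01 drugs given over the same 120 h give 120 + 120 = 240 h, while the time on at least one antibiotic is 120 h. Separately, take a course with a known start 48 h before first dose and an end 72 h after it. End minus start gives 48 + 72 = 120 h, and truncation at first intake gives 72 h. The window wording and the reference to hospital stay, which does truncate, point to 72 h. The explicit antibiotic rule covers only unknown start datetimes.

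**The case against.** A reader might infer that neither endpoint measures anything pimodivir could change. The documents do not support that. Incidence still captures every new start among subjects not on antibiotics at first dose. Carry-over use predates study drug and is balanced in expectation by randomization, so it costs sensitivity but does not bias the comparison or inflate type I error. Duration is already confined to the period after first intake, and stopping an ongoing course earlier is something treatment could affect.

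Further points carry weight:

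- Protocol 2.1.1 only sets out to investigate antibiotic use, and 2.1.2 does not limit it to new starts. Any use after first dose is a legitimate endpoint.
- Neither endpoint is in the seven-endpoint confirmatory sequence, and neither was powered, so low power here is not a failure of the plan.
- The size rests wholly on assumed rates. A ceiling effect is possible but not established.
- Double counting of concurrent drugs depends on how separate events is read. It is an ambiguity, not a settled error.
- Restricting to non-users is costly at high b, leaving 90 or 30 per arm at 70% or 90%, and it leaves out baseline users who later need a new antibiotic.
- The SAP has related outputs: tabulations of antibiotics given for adverse events reported as influenza complications (4.6), and logistic regression of adjudicated infectious complications (5.3.2.1).

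All of this lowers the priority. It does not supply a between-arm analysis of antibiotics started after first dose, and it does not give the duration derivation a rule for overlap.

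**Conclusion.** The point holds as a loss of sensitivity in incidence and a gap in the duration derivation. Reading SAP 5.3.1.1 with 4.6, antibiotics running at first dose and continued count as Yes, with all subjects in the denominator and no adjustment for baseline use. The risk difference in new starts shrinks by the factor 1 − b. In the assumed scenarios with b from 50% to 90%, power as written is half or less of that in non-users, and at b = 0 nothing is lost. Those figures assume 300 analysed per arm, equal b in both arms, the stated new-start rates, and unadjusted two-proportion tests in place of the Firth model. The true size is unknown until b is known.

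For duration, the text permits a calculation that returns 240 h for 120 h on treatment, and it leaves truncation of known pre-dose starts to inference. No confirmatory claim depends on either endpoint, so this is an inexpensive improvement of modest priority.

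**What to change.** 1. Keep the all-subject incidence endpoint and add a parameter for an antibiotic started post-baseline, in line with those for ICU admission and ventilation. A J01 drug first started after first study drug intake would count, including in subjects already on another antibiotic.
2. Add antibiotic use at first dose (yes/no) as a covariate in the incidence models, or report incidence by that baseline group. The group is fixed before study drug, so the split does not condition on an outcome.
3. Define duration as the union of time on at least one J01 drug, merging overlapping records.
4. State that every record starting before first intake is truncated at first intake, whether or not the start datetime is known.

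The cost is SAP wording and one more derived variable, programmed from start and end datetimes already collected. Any analysis restricted to baseline non-users has fewer subjects, which is why the all-subject endpoint should stay.

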4.1. Inclusion Criteria

Each potential subject must satisfy all of the following criteria to be enrolled in the study:

1. Male or female, 13 to 85 years of age, inclusive. Note: Adolescent subjects (13 to 17 years) will be enrolled in selected countries and study sites consistent with local regulations.
2. Tested positive for influenza A infection after the onset of symptoms using a polymerase chain reaction (PCR)-based or other rapid molecular diagnostic assay.

3. Requires hospitalization to treat influenza infection and/or to treat complications of influenza infection (eg, radiological signs of lower respiratory tract disease, septic shock, central nervous system [CNS] involvement, myositis, rhabdomyolysis, acute exacerbation of chronic kidney disease, severe dehydration, myocarditis, pericarditis, ischemic heart disease, exacerbation of underlying chronic pulmonary disease, including asthma, chronic obstructive pulmonary disease [COPD], decompensation of previously controlled diabetes mellitus), including subjects admitted to the ICU. Note: For the purpose of the protocol, subjects admitted under “observation” status with an anticipated length of stay beyond 24 hours are eligible for enrollment.
4. Enrollment and initiation of study drug treatment ≤ 96 hours after onset of influenza symptoms.
5. Being on invasive mechanical ventilation or having a peripheral capillary oxygen saturation (SpO₂) $< 94\%$ on room air during screening. Subjects with known pre-influenza SpO₂ $< 94\%$ must have an SpO₂ decline $\geq 3\%$ from pre-influenza SpO₂ during screening.
6. Having a screening/baseline NEWS2 of ≥ 4 .
7. Must sign an ICF (or their legally acceptable representative (LAR) must sign on behalf of the subject to participate in the study for minors and incapacitated subjects, as permitted by local regulatory authorities, IRB/IECs, and local laws) indicating that he or she understands the purpose of, and procedures required for, the study and is willing to participate in the study. Assent is also required of adolescents capable of understanding the nature of the study.

Note: A number of subjects eligible for this study may be acutely incapacitated and not able to consent due to their medical condition (eg, too weak or debilitated, unconscious, experiencing severe shortness of breath, or mechanically ventilated). These subjects can be included as permitted by local regulatory authorities, IRB/IEC, and local laws.

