2.5. Baseline and Endpoint

The baseline analysis visit is defined as the last assessment before the first intake of the study drug, with the possible exception for height, weight, viral load results from the central lab testing and the hospital recovery scale (HRS). Height and weight are only recorded once, at screening/baseline visit, and the values recorded at this visit will be allocated to the baseline analysis visits irrespective of start of study drug. For viral load, if no measurement is available prior to first dose of study drug, then the first result from the central lab testing obtained up to and including 30 minutes after first dose of study drug will be considered as the baseline assessment and will be flagged in the analysis dataset. The baseline HRS is defined irrespective of the time of the start of study drug, and is covering the screening/baseline/day 1 visit which may be performed over two days as defined per protocol. Baseline HRS will be assigned to Day 1.

As specified in the protocol, an ECG recording within 1 calendar day before signing of the ICF/assent form can be used as baseline ECG requirement, if no ECG measurement was performed between signing ICF and first study drug intake.

For programming purposes the baseline record will be doubled in the ADAM datasets, the doubled record will be renamed with AVISIT = 'Baseline', AVISITN = 0 and will be assigned to the treatment phase.

For vital signs, NEWS2, ECG and central laboratory data the last study visit (Endpoint) is defined as the last scheduled study visit/timepoint and will be either the final study visit (day 28) or the safety follow-up visit.

For viral phenotyping, the last visit (Endpoint) is defined as the last study visit/timepoint for which an EC₅₀ and/or IC₅₀ result is available (including unscheduled visit results).

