5.2. Primary Efficacy Endpoint(s)

5.2.1. Definition

The primary efficacy analysis will be based on the ITT-i analysis set and consists of the analysis of the hospital recovery scale outcome on Day 6.

The hospital recovery scale provides 6 mutually exclusive conditions ordered from best to worst, and the score reflects the subject’s worst situation on the day of assessment:

1. Not hospitalized
2. Non-ICU hospitalization, not requiring supplemental oxygen
3. Non-ICU hospitalization, requiring supplemental oxygen
4. Admitted to the ICU, not requiring invasive mechanical ventilation
5. Requiring invasive mechanical ventilation
6. Death

The hospital recovery scale categories are defined below. For ease of categorization, the categories are defined from worst to best. A subject will be evaluated in the same ordering of the categories as below. Once a subject fulfils the criteria for a category, the category is assigned to the subject and the evaluation stops.

6. Death

- Subject died at any time on the day of assessment or earlier (all-cause mortality).

5. Requiring invasive mechanical ventilation

- Any oxygen support requiring intubation or extracorporeal oxygenation
- Invasive mechanical ventilation is used at any time on the day of assessment.

4. Admitted to the ICU, not requiring invasive mechanical ventilation

Subject met either of the 2 following criteria:

- In the ICU (and ICU level of care is required during the day of assessment)
- On the hospital ward, with or without supplemental oxygen, but deemed to require ICU level of care at any time during the day of assessment (e.g., not transferred to ICU due to bed availability)

Requiring ICU level of care is defined by:

- Some specific conditions:
 - Treatment of acute unstable arrhythmias
 - Treatment of complicated acid-base or electrolyte imbalances
 - Large volume resuscitation
 - Utilization of intravenous vasoactive medications
 - S/P cardiac arrest
 - Cardiogenic Shock
 - Acute myocardial infarct with complications
 - Cardiac tamponade
 - Acute congestive heart failure
 - Acute or imminent respiratory failure
 - Hemodynamic instability

- Diabetic ketoacidosis complicated by hemodynamic instability, altered mental status, respiratory insufficiency, or severe acidosis
 - Other conditions requiring specialized equipment and/or staff competencies only available in the ICU
3. Non-ICU hospitalization, requiring supplemental oxygen

Subject met either of the 2 following criteria:

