Time to clinical failure (days) [Time-to event]	
The time (in days) from first study drug intake to first clinical failure(=event).
 
Clinical failure is defined as having one of the following events
 
 • HRS >3 
The first event will be considered. In case mechanical ventilation is started multiple times, only the first start of mechanical ventilation after first study drug intake is used.
 
Subjects without a clinical failure at the time of completion or at the time of withdrawal from the study will be censored at the date of completion or withdrawal.
 
(Date of event or censoring— date of first dose of study drug) + 1

Incidence of Mortality per day	Number and percentage of subjects that died and cumulative number and percentage of subjects that died per day after first study drug.

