ATTACHMENT 6. : HRS DERIVATION

The HRS categories should be evaluated from 6 to 1. First check if the subject falls in category 6 (has the subject died?) if not then we evaluate category 5, if not 5 then evaluate category 4 and so on.

The HRS is evaluated at baseline and per day, relative to the first study drug intake.

The baseline HRS is covering the full baseline/screening/day 1 visit which can occur on 2 days.

Timing of first study drug intake is not taken into account.

Note:

- VSOXYSAT is assessed 3 times per day (or per baseline visit). In case one of the assessments says 'N' then the final result for that day (or baseline visit) is 'N', else if one of the assessments is 'NA' then the final result is 'NA' else if one of the assessments is missing then final result is missing.

So a combination of 'Y', "", "N" → result ='N'

'Y', "", "NA" → result ='NA'

'Y','Y','' → result =''

'Y','Y','Y' → result ='Y'

On the baseline visit, on days at or after HO end date or on the day of discontinuation it might be that less than 3 assessments are done. Therefore, take only the records into account from the dataset on those days as planned. The same rules above apply to derive the final result per day when more than 1 assessment is collected.

- In case the subject withdrew from the study, the HRS will be set to missing from the next day onwards.
- In case of chronic oxygen use and multiple CMARTN values on a day we consider the worst value: In case one of the values is 'N' then final result for that day (or baseline visit) is 'N', else if one of the assessments is missing then final result is missing.
- The list of types of supplemental oxygen and invasive mechanical ventilation can be extended depending on the medical review (see DPS part 2 or Excel sheet of the medical review)
- The list of hospitalization terms (i.e.: ICU or WARD) can be extended depending on the medical review (see DPS part 2 or Excel sheet of the medical review).
- If the Subjects has no HO data, the subject is considered to be in the hospital during the trial. All other aspect of the HRS will be evaluated according to the derivation below.
- In case the readiness for discharge (RDISHOSP) is assessed more than once per day (baseline visit) we consider the worst value: in case one of the values is 'N' then the final result of that day (or baseline visit) is 'N'

Some clarification is required for following categories:

6. Death

When DM.DTHDTC<=(date of assessment)

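### Time to clinical failure is defined as any HRS above 3 with no reference to baseline, so subjects who enter at HRS 4 or 5 can fail on Day 1 or 2 without having worsened

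*SAP*

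**What the plan says.** **The endpoint (SAP 5.3.1.1).** The clock starts at first intake: "The time (in days) from first study drug intake to first clinical failure(=event". The text continues "Clinical failure is defined as having one of the following events" and lists a single item, an HRS above 3. Time is the event or censoring date minus the "date of first dose of study drug) + 1", so an event on the day of first dose has time 1, the smallest possible value. A further sentence reads "In case mechanical ventilation is started multiple times, only the first start of mechanical ventilation after first study drug intake is used". Nothing requires the event to be new or worse than baseline, and no subject is excluded for being above 3 at entry.

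**The scale (SAP 5.2.1).** Category 4 is "Admitted to the ICU, not requiring invasive mechanical ventilation", 5 is invasive ventilation and 6 is death. Each day is scored at its worst.

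**Who is enrolled (Protocol 4.1).** Criterion 3 covers hospitalized subjects, "including subjects admitted to the ICU". Criterion 5 accepts invasive mechanical ventilation as one way to qualify.

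**Where baseline sits.** SAP 2.5: "Baseline HRS will be assigned to Day 1". Attachment 6 adds, for the baseline score, "Timing of first study drug intake is not taken into account".

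**The analysis (SAP 5.3.2 and 5.3.2.1).** Time-to-event clinical outcomes use a stratified Gehan-Wilcoxon test as primary, with log-rank, Kaplan-Meier, AFT and Cox analyses. The AFT and Cox models include the stratification factors but not baseline HRS. The primary HRS model in SAP 5.2.3 does include it.

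**The concern.** An endpoint called clinical failure should show who deteriorates after starting treatment. Under this rule, part of what it shows is who was already in category 4 or 5 at randomization. Those events fall at the earliest possible times. Randomization should spread them evenly between arms, so bias towards either arm is not the main worry. The worry is dilution: events that largely reflect entry status swell the event count in both arms and pull the treatment ratio towards 1. A reader of the Kaplan-Meier curve would also see an early drop that is not deterioration.

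It looks like an oversight. In the same section, post-baseline ICU admission and ventilation started post-baseline both treat baseline status separately.

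**Working it through.** **1. The plan's own figure.** No power or event count is stated for this endpoint. The only planning figure is 600 subjects for 90% power on the primary endpoint, and it reproduces. With OR 0.62 and placebo shares 30/30/25/5/5/5%, Whitehead's n per arm = 6(1.960 + 1.282)² / (ln 0.62)² / (1 − Σp̄³) = 300.7, or 601 in total. Power at 600 is 89.9%. It has no bearing on time to clinical failure.

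**2. The rule applied to a subject entering at HRS 5.**

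| Course | Day 1 HRS counts | Only Day 2 onward counts |
|---|---|---|
| 5 on Day 1, 3 or better from Day 2 | fails, time = 0 + 1 = 1 | no failure unless later above 3 |
| 5 on Day 1, 4 on Day 2, then recovers | fails, time 1 | fails, time 1 + 1 = 2 |
| Extubated during Day 2 | fails, time 1 | fails, time 2 (worst status of the day is 5) |

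**3. Size, simple version.** All inputs here are assumptions: a share f at HRS 4 or 5 at baseline, all counted as failures; new-failure risks of 15% (placebo) and 10% (pimodivir) in the rest; 300 per arm. The nearest planning figure is 5 + 5 + 5 = 15% of placebo subjects above HRS 3 on Day 6 (SAP 1.4). That is a Day 6 prevalence, deaths included, and not a new-failure risk.

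- Everyone: compare f + (1 − f)·0.15 with f + (1 − f)·0.10, n = 300 per arm.
- At-risk subjects only: compare 0.15 with 0.10, n = 300(1 − f) per arm.
- z = difference / √(2·p̄(1 − p̄)/n).

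For f = 20%, everyone: 0.32 vs 0.28, p̄ = 0.30, z = 0.04/√(2·0.21/300) = 1.07. At-risk only: n = 240, p̄ = 0.125, z = 0.05/√(2·0.1094/240) = 1.66. Power is 19% against 38%.

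| f | Proportions, everyone | z, everyone | n per arm at risk | z, at-risk only |
|---|---|---|---|---|
| 10% | 0.235 vs 0.190 | 1.35 | 270 | 1.76 |
| 20% | 0.320 vs 0.280 | 1.07 | 240 | 1.66 |
| 30% | 0.405 vs 0.370 | 0.88 | 210 | 1.55 |

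This ignores timing and the planned stratification.

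**4. Size, with timing.** An illustrative simulation used 600 subjects, 1:1, unstratified tests at two-sided 5%, a true hazard ratio of 0.50 for new failure, follow-up to Day 14 and 1,500 replicates. Subjects above HRS 3 at baseline were given an event at time 1, which is the Day 1 reading. Shares and risks are again assumed.

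| Baseline share | Placebo new-failure risk | Day 1 events as share of all events | Estimated HR, rule as written | Gehan power, new failures only | Gehan power, rule as written |
|---|---|---|---|---|---|
| 5% | 10% | 41% | 0.67 | 60% | 37% |
| 5% | 20% | 26% | 0.60 | 88% | 76% |
| 10% | 10% | 60% | 0.75 | 57% | 25% |
| 10% | 20% | 42% | 0.67 | 86% | 58% |
| 15% | 10% | 70% | 0.80 | 53% | 18% |
| 15% | 20% | 54% | 0.71 | 86% | 46% |
| 25% | 10% | 82% | 0.85 | 53% | 11% |
| 25% | 20% | 69% | 0.78 | 80% | 26% |

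With new failures only, the estimated HR stays at 0.50 to 0.51. Gehan-Wilcoxon weights each event time by the number at risk. At a 10% share the weight is 600 at time 1 and at most 540 afterwards. In that row at 20% risk, power under the rule as written is 58% for Gehan against 65% for log-rank.

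**The case against.** **The text may intend new onset.** The ventilation sentence refers to the first start after intake, and the daily HRS outcomes are defined from Day 2. If only Day 2 onward counts, a subject who steps down to HRS 3 or better by Day 2 does not fail, and treatment could influence that. This stands as a limit: the SAP does not settle the Day 1 question. It does not remove the problem, because a subject still at 4 or 5 on Day 2 fails while improving. The ventilation sentence also gives no rule for someone ventilated at entry.

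**Stratification helps.** The planned test is stratified by NEWS2. The imputed values for invasively ventilated subjects in SAP 7.6.1 score 3 + 2 + 3 = 8 in the cases they cover, which places those subjects in the stratum of 6 or more. So the unstratified figures do not describe the planned test exactly. But that stratum does not isolate HRS 4 or 5, since subjects at HRS 3 or below can also score 6 or more.

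**Deterioration is covered elsewhere.** Post-baseline ICU admission, ventilation started post-baseline and baseline-to-day HRS shift tables are all reported. They limit the harm but do not repair this endpoint.

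**Stronger readings a reader might infer.**
- That everyone in the ICU or on any ventilation fails at once. An ICU stay without medical need scores 2 or 3 (SAP 5.2.1), and non-invasive mechanical ventilation is listed under category 3 (Attachment 6).
- That the early events carry no treatment information at all. This fails under the Day 2 reading, as above.
- That odds ratios are diluted. None is planned for this endpoint.

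**Conclusion.** The point holds for subjects at baseline HRS 4 or 5. As written, they fail at time 1, or at time 2 if Day 1 is excluded and they are still above 3, whether or not they have worsened. The planned AFT and Cox models do not correct for this.

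The direction of the effect is clear and its size is not. Under the assumed inputs, z falls from 1.76 to 1.35 at a 10% baseline share and from 1.55 to 0.88 at 30%. In that example the result is non-significant either way. In the simulation, a true hazard ratio of 0.50 is estimated at 0.60 to 0.85. These figures rest on baseline shares and failure risks that the documents do not give, and on unstratified tests. The simulation covers only the Day 1 reading.

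A reader might infer a threat to the confirmatory results, but the documents do not support that. The endpoint was added in SAP Amendment 1 and is not among the seven endpoints tested hierarchically in SAP 5.1.1. Type I error, sample size and the primary claim are unaffected. What suffers is the interpretability and sensitivity of one secondary endpoint.

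**What to change.** Amend the definition in SAP 5.3.1.1 in one of two ways:

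1. Restrict the analysis to subjects with baseline HRS 3 or below, with the event being the first post-baseline HRS above 3. This is the cleaner measure of new failure; the cost is fewer subjects.
2. Keep all subjects and define failure as a post-baseline worsening from baseline into a higher HRS category above 3, or death.

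Under either, state that the Day 1 baseline HRS is not an event, and reconcile the sentence on the first start of mechanical ventilation with the HRS rule. If all subjects are kept, adding baseline HRS to the AFT and Cox models for this endpoint would match the primary model. The cost is SAP wording and programming; no new data are needed.
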